18.2 Data Display Specifications

18.2.1 Table Outlines

Template T_SD1

Table 10.1 Summary of subject disposition

Population	Status	Reason for Withdrawal	Treatment 1 (N=xx) n (%)	Treatment 2 (N=xx) n (%)	Etc	All Subjects n (%)	
Safety	Included		xx	xx		xx	
	Completed		xx (xx)	xx (xx)		xx (xx)	
	Withdrawn		Death	xx (xx)	xx (xx)		xx (xx)
			Adverse Events	xx (xx)	xx (xx)		xx (xx)
			Withdrawal by subject	xx (xx)	xx (xx)		xx (xx)
			Study terminated by Sponsor	xx (xx)	xx (xx)		xx (xx)
			Lost to follow-up	xx (xx)	xx (xx)		xx (xx)
			Other	xx (xx)	xx (xx)		xx (xx)
			Alternative 1 (if applicable)	Included			
	Alternative 2 (if applicable)	Included					

Source: Listing 16.2.xx

Programming notes: Continued with all treatment groups

Template T_DM1

Table 14.1 Summary of demographic characteristics

Variable	Statistics	Treatment 1 (N=xx)	Treatment 2 (N=xx)	Etc	All Subjects (N=xx)
Age (y)	n				
	Mean				
	SD				
	Median				
	Min				
	Max				
Gender	Male				
Race (%)	American Indian or Alaskan				
	Native				
	Asian				
	Black				
	Native Hawaiian or other				
	Pacific Islander				
	White				
	Other				
Ethnicity (%)	Hispanic or Latino				
	Not Hispanic or Latino				
Height (cm)	n				
	Mean				
	SD				
	Median				
	Min				
	Max				
Weight (kg)	n				
	Mean				
	SD				
	Median				

Variable	Statistics	Treatment 1 (N=xx)	Treatment 2 (N=xx)	Etc	All Subjects (N=xx)
BMI (kg/m ²)	Min				
	Max				
	n				
	Mean				
	SD				
	Median				
Smoker (%)	Min				
	Max				
	n				
	Mean				
	SD				
	Median				
Cigarettes* (daily)	Min				
	Max				
	n				
	Mean				
	SD				
	Median				
Alcohol* (units/week)	Min				
	Max				
	n				
	Mean				
	SD				
	Median				
Xanthine* (units/week)	Min				
	Max				
	n				

*includes only those subjects who smoke/drink alcohol/drink beverages containing Xanthine

Source: Listing 16.2.xx

Programming notes: Continued with all treatment groups and additional demographic characteristics

Template T_PK1

Table 14.2.xx Summary of emodepside plasma pharmacokinetic concentration-time data [units]

Treatment	{Add. time var.}	Planned Relative Time	n	No. Imputed	Mean	95% CI (Lower,Upper)	SD	%CVb	Median	Min	Max	Geom. Mean	Geom. SD
Treatment 1 (N=xx)		Pre-dose	x	x	xxxx.x	(xxxx.x,xxxx.x)		xx.x	xxxx.x	xxxx	xxxx		
		30 min	x	x	xxxx.x	(xxxx.x,xxxx.x)	xx.xx	xx.x	xxxx.x	xxxx	xxxx		
		1 hr	x	x	xxxx.x	(xxxx.x,xxxx.x)	xx.xx	xx.x	xxxx.x	xxxx	xxxx		
Treatment 2 (N=xx)		Pre-dose	x	x	xxxx.x	(xxxx.x,xxxx.x)	xx.xx	xx.x	xxxx.x	xxxx	xxxx		
		30 min	x	x	xxxx.x	(xxxx.x,xxxx.x)	xx.xx	xx.x	xxxx.x	xxxx	xxxx		
		1 hr	x	x	xxxx.x	(xxxx.x,xxxx.x)	xx.xx	xx.x	xxxx.x	xxxx	xxxx		

Source: Listing 16.2.xx

Programming notes: Continued with all dose levels and timepoints

Template T_PK3

Table 14.2.xx Summary of derived emodepside plasma pharmacokinetic parameters

Parameter	Treatment	{Additional time variables}	n	Mean	95% CI (Lower,Upper)	SD	%CVb	Median	Min	Max
AUC _t (units)	Treatment 1 (N=xx)		xx	xxxx.xx	(xxxx.xx,xxxx.xx)	xx.xxx	xx.x	xxxx.xx	xxxx.x	xxxx.x
	Treatment 2 (N=xx)		xx	xxxx.xx	(xxxx.xx,xxxx.xx)	xx.xxx	xx.x	xxxx.xx	xxxx.x	xxxx.x
C _{max} (units)	Treatment 1 (N=xx)		xx	xxxx.xx	(xxxx.xx,xxxx.xx)	xx.xxx	xx.x	xxxx.xx	xxxx.x	xxxx.x
	Treatment 2 (N=xx)		xx	xxxx.xx	(xxxx.xx,xxxx.xx)	xx.xxx	xx.x	xxxx.xx	xxxx.x	xxxx.x

Source: Listing 16.2.xx

Programming notes: Continued with all dose levels, timepoints and parameters

Template T_PK4

Table 14.2.xx Summary of log-transformed derived emodepside plasma pharmacokinetic parameters

Parameter	Treatment	{Additional time variables}	n	Geom Mean	95% CI (Lower,Upper)	SD (logs)	%CV _b
AUC _{last} (units)	Treatment 1 (N=xx)			xxxx.xx	(xxxx.xx,xxxx.xx)	xx.xxx	xx.xx
	Treatment 2 (N=xx)			xxxx.xx	(xxxx.xx,xxxx.xx)	xx.xxx	xx.xx
C _{max} (units)	Treatment 1 (N=xx)			xxxx.xx	(xxxx.xx,xxxx.xx)	xx.xxx	xx.xx
	Treatment 2 (N=xx)			xxxx.xx	(xxxx.xx,xxxx.xx)	xx.xxx	xx.xx

Source: Listing 16.2.xx

Programming notes: Continued with all dose levels, timepoints and parameters

Template T_AE1

Table 14.3.3.xx Summary of treatment-emergent adverse events

System Organ Class	Preferred Term	Treatment 1 (N=xx) n (%)	Treatment 2 (N=xx) n (%)	Etc
Number of subjects with AEs		x (xx.x)	x (xx.x)	
Gastrointestinal disorders	Total number of subjects	x (xx.x)	x (xx.x)	
	Abdominal discomfort	x (xx.x) [xx]	x (xx.x) [xx]	
	Abdominal pain	x (xx.x) [xx]	x (xx.x) [xx]	
	↓			
Nervous system disorders	Total number of subjects			
	Dizziness			
	Headache			
	↓			
	↓			

n = number of subjects (subjects with ≥1 adverse event are counted only once per system organ class and preferred term)

[] = number of adverse events

Based on MedDRA version xx.x

Source: Listing 16.2.xx

Programming notes: Continued with all treatment groups
 SOC and PTs are sorted in decreasing order of frequency
 Presented for all applicable MedDRA system organ classes and terms.

Template T_AE3

Table 14.3.3.xx Summary of treatment-emergent adverse events by severity

System Organ Class	Preferred Term	Treatment 1 (N=xx) n (%)	Treatment 2 (N=xx) n (%)	Etc
Number of subjects with AEs		x (xx.x)	x (xx.x)	
Gastrointestinal disorders	Abdominal discomfort	x (xx.x)	x (xx.x)	
	Abdominal pain	x (xx.x)	x (xx.x)	
	↓			
Nervous system disorders	Dizziness			
	Headache			
	↓			
↓	↓			

n = number of subjects (subjects with ≥1 adverse event are counted only once per system organ class and preferred term)

Based on MedDRA version xx.x

Source: Listing 16.2.xx

*Programming notes: Each preferred term counted only once across all severities for each subject/treatment
 Continued with all treatment groups
 SOCs and PTs are sorted in decreasing order of frequency
 Presented for all applicable MedDRA system organ classes and terms.*

Template T_LB1

Table 14.3.4.xx Summary of laboratory values of potential clinical importance

Laboratory Test (units)	Treatment	Planned Relative		Double Flags	
		Time	n	HI	LD
Treatment 1 (N=xx)					

H = Above reference interval, L = Below reference interval, I = Increase from baseline greater than pre-defined limit, D = Decrease from baseline greater than pre-defined limit

Source: Listing 16.2.xx

Programming notes: Continued with all tests, treatment groups and time points. n = total number of results for that parameter

Template T_LB2

Table 14.3.5.xx Summary of chemistry laboratory values

Laboratory Test (units)	Treatment	Planned Relative Time	n	Mean	SD	Median	Min	Max	n	Change from Baseline					
										Mean	SD	Median	Min	Max	
Treatment 1 (N=xx)															

Source: Listing 16.2.xx

Programming notes: Continued with all treatments and time points

Template T_UR1

Table 14.3.5.xx Summary of urinalysis results

Laboratory Test	Planned Relative Time	Result	Treatment 1 (N=xx)		Treatment 2 (N=xx)	
			n	%	n	%
Time 1		Positive	X	x		
		Negative	X	X		
		Not Done	x			
Time 2		Positive				
		Negative				
		Not Done				

Source: Listing 16.2.xx

Programming notes: Results recorded as received, e.g. Negative, Trace, etc; urine pH summarised as <5, 5-8, >8; specific gravity summarised as <=1.005, 1.006 - 1.010, 1.011 - 1.015, 1.016 - 1.020, 1.021 - 1.025, 1.026 - 1.029, >=1.030. Continued with all treatment groups and time points. The n's sum to N but the calculated percentages exclude Not Done.

Template T_VS1

Table 14.3.6.xx Summary of vital signs

Variable (units)	Treatment	Planned Relative Time	n	Mean	SD	Median	Min	Max	Change from Baseline					
									n	Mean	SD	Median	Min	Max
Systolic BP (mmHg)	Treatment 1 (N=xx)													

Source: Listing 16.2.xx

Programming notes: Continued with all variables, treatments and time points

Template T_EG2

Table 14.3.7.xx Summary of ECG values

Variable (units)	Treatment	Planned Relative							Change from Baseline					
		Time	n	Mean	SD	Median	Min	Max	n	Mean	SD	Median	Min	Max
Heart Rate (bpm)	Treatment 1 (N=xx)													
	Treatment 2 (N=xx)													
PR Interval (msec)	Treatment 1 (N=xx)													
	Treatment 2 (N=xx)													

Source: Listing 16.2.xx

Programming notes: Continued with all treatment groups and time points
 Do not summarise RR or QRS axis

Template T_EG3

Table 14.3.7.xx Summary of ECG values and changes in ECG values of potential clinical importance

Variable	Treatment	Planned Relative Time	451 – 480 msec		481 – 500 msec		> 500 msec		>30-60 msec Increase		>60 msec Increase	
			n	%	n	%	n	%	n	%	n	%
QT interval	Treatment 1 (N=xx)	Time 1										
		Time 2										
		Time 3										
	Treatment 2 (N=xx)	Time 1										
		Time 2										
		Time 3										
QTcF interval	Treatment 1 (N=xx)	Time 1										
		Time 2										
		Time 3										

[figure not shown]
Source: Listing 16.2.xx

Programming notes: Continued with all treatments and time points. n = total number of results for that parameter

18.2.2 Figure Outlines

Template F_PK1

[figure not shown]
Figure 14.2.xx Individual emodepside plasma concentration-time plots (linear and semi-log)

Programming notes: For parallel group studies with a multiple days, page by treatment and include one subject with both days on same page

Template F_PK2

Figure 14.2.xx Geometric Mean (with Geo SD error bars) emodepside plasma concentration-time plots (linear and semi-log)

[figure not shown]
[figure not shown]

BLQ values observed post dose are imputed to half of the LLOQ. Pre dose values are imputed to zero

Programming notes: *Offset treatment groups (to both sides of timepoint) to minimise overlapping error bars*

[figure not shown]
Template F_PK10

Figure 16.2.xx Individual emodepside plasma concentration-time plots for estimation of lambda-z, with regression line

Template F_SAF1

Figure 14.3.1 Individual systolic blood pressure-time plots

*Programming note: Plots are by treatment groups
Continue with all parameters*

18.2.3 Listing Outlines

Template L_SD1_PG

Listing 16.2.x.xx Listing of study dates

Treatment	Subject	Screening	First Dose	Final Follow Up
-----------	---------	-----------	------------	--------------------

Programming notes: Lists dates for screening, each dosing period and follow up

Template L_SD2_PG

Listing 16.2.x.xx Listing of reasons for withdrawal

Treatment	Subject	Date of Withdrawal	Study Day	Reason
-----------	---------	-----------------------	--------------	--------

Programming notes: Reason for withdrawal is concatenation of reason and details

Template L_DV1_PG

Listing 16.2.x.xx Listing of subjects with inclusion/exclusion criteria deviations

Treatment	Subject	Type	Criterion
		Inclusion	
		Exclusion	

Template L_TD1_PG

Listing 16.2.x.xx Listing of subjects with time deviations

Treatment	Subject	Planned Relative Time	Procedure	Allowed deviation (h:min)	Actual deviation (h:min)	Time outside the deviation window (h:min)
-----------	---------	-----------------------------	-----------	---------------------------------	--------------------------------	---

Programming notes: Only include time deviations which exceed the allowed deviation

Template L_DV2_PG

Listing 16.2.x.xx Listing of subjects with other protocol deviations

Treatment	Subject	Protocol Deviation
-----------	---------	--------------------

Template L_AN1_PG

Listing 16.2.x.xx Listing of analysis populations

Treatment	Subject	Safety Population	Population 1	Population 2	Etc.
-----------	---------	----------------------	--------------	--------------	------

Template L_DM1_PG

Listing 16.2.x.xx Listing of demographic characteristics

Treatment	Subject	Date of screening visit	Age (y)	Gender	Race	Ethnic origin	Height (cm)	Weight (kg)	BMI (kg/m ²)	Etc (units)
Treatment 1										

↓

Programming notes: A by-subject listing of demographic characteristics including:

Treatment

Subject

Date of screening visit

Age

Gender

Race / Ethnic Origin

Height (if collected only once during the study)

Weight (if collected only once during the study)

Smoking History

Alcohol Consumption

Xanthine

Additional study-specific demography characteristics included on the CRF

Template L_CM1_PG

Listing 16.2.x.xx Listing of concomitant medications

Treatment	Subject	ATC Class/ Medication Code*	Drug Name/ Indication	Dose/ Freq/Route	Date/time Started/ Date Stopped	Time Since Last Dose	Started Pre- Trial?	Ongoing Medication?
-----------	---------	--------------------------------	--------------------------	---------------------	------------------------------------	-------------------------	------------------------	------------------------

Coded using WHODrug Global version xx.x*

*Programming notes: * only include this column and the footnote if coding used
 Include dose and units (e.g. 5 mg)/Freq/Route*

Template L_EX1_PG

Listing 16.2.x.xx Listing of exposure data

Treatment	Subject	Start Date/ Start Time of Dose	Stop Date/ Stop Time of Dose	Duration (days)	Dose Dose Unit	Formulation/ Route	Frequency
Treatment 1	1001	01JAN2002 23:59	15FEB2002 15:30	46	25 mg	Tablet/ Oral	2xday

Template L_PK1_PG

Listing 16.2.6.xx Listing of emodepside plasma pharmacokinetic concentration-time data

Treatment	Subject	{Add. time var.}	Date	Study Day	Planned Relative Time	Actual time (hh:mm)	Time Deviation (min)	Actual Relative Time (h)	Concentration (units)
-----------	---------	------------------------	------	-----------	--------------------------	------------------------	-------------------------	---------------------------------	-----------------------

Below the Limit of Quantification (BLQ) is < xx units (e.g. 1 ng/mL)

Programming notes: Values below LLOQ are shown as BLQ. Check LLOQ value in final PK spreadsheet for each analyte.

Template L_PK2_PG

Listing 16.2.6.xx Listing of emodepside urine sample collections

Treatment	Subject	{Add. time var.}	Study Day	Planned Relative Time	Start Date/ Start Time	Stop Date/ Stop Time	Conc. (units)/ Volume (units)	Amount excreted (units)	Cumulative amount excreted	
									Absolute (units)	Relative to dose (%)
				Pre-dose			xxx.xx/ xxx.xx	xxx.xx		
				0-12 h			xxx.xx/ xxx.xx	xxx.xx	xxx.xx	x.xx
				12-24 h			xxx.xx/ xxx.xx	xxx.xx	xxx.xx	x.xx

Programming notes: Planned relative time is in the form "0h to 12h" For spot samples (pre dose and follow up) only report urine concentrations and volumes.

Template L_PK4_PG

Listing 16.2.xx Listing of derived emodepside plasma pharmacokinetic parameters

Treatment	Subject	{Add. time var.}	AUC _{inf} (units)	AUC _t (units)	C _{max} (units)	t _{1/2} (units)	t _{max} (units)
-----------	---------	------------------	----------------------------	--------------------------	--------------------------	--------------------------	--------------------------

Programming notes: Continue with all parameters

Template L_AE1_PG

Listing 16.2.x.xx Listing of all adverse events

Treatment	Subject	System Organ Class / Preferred Term/ Verbatim Text	Outcome/ Onset Date/Time/ Resolved Date/Time/ Duration	Time Since Last Dose	Severity/ Serious/ Withdrawal	Frequency/ Action Taken (1)/ Other Action Taken	Related to Study Drug/ Treatment Emergent?
Treatment 1	1001	Gastrointestinal Disorders / Intestinal Spasm / Entero-spasm	Resolved/ 24SEP2003 13:05/ 27OCT2003 7:50/ 34d 4h 5m	10d 7h 3m	Mild/ No/ Yes	Intermittent/ Dose not changed/ None	Possibly/ Yes

(1) Action Taken with Study Treatment

Programming notes: For the listing of "other significant AEs" include (from ICH E3) AEs leading to withdrawal, AEs leading to dose reduction (including drug withdrawn, interrupted, reduced or similar) and AEs with AEOSE=Y. If AEOSE has not been collected then use "Otherwise significant" in the CRF.

Template L_LB1_PG

Listing 16.2.x.xx Listing of clinical chemistry abnormalities of potential clinical importance

Treatment	Subject	Laboratory test (units)	Planned Relative Time	Date/Time	Study Day	Value	Reference Interval	RI	BL	Clinically Significant?
Treatment 1	1001	Alk Phos (U/L)	Time 1	01JAN2002 13:34	-1	64.00	32.0 - 92.0			
			Time 2	01APR2002 07:22	85	84.00	32.0 - 92.0			
		ALT (U/L)	Time 1	01JAN2002 18:56	-1	29.00	10.0 - 40.0			
			Time 2	01APR2002 09:22	85	70.00	10.0- 40.0	H	I	Y

RI for Reference Interval flag, BL for Change from Baseline flag;

H = Above reference interval, L = Below reference interval, I = Increase from baseline greater than pre-defined limit, D = Decrease from baseline greater than pre-defined limit

Programming notes: Lists only double-flagged subjects

Template L_LB2_PG

Listing 16.2.x.xx Listing of all clinical chemistry laboratory data for subjects with PCI abnormalities

Treatment	Subject	Planned Relative Time	Date/Time	Alkaline Phosphatase (IU/L)			Alanine Amino Transferase (IU/L)			Aspartate Amino Transferase (IU/L)			Total Bilirubin (UMOL/L)		
				Result	RI	BL	Result	RI	BL	Result	RI	BL	Result	RI	BL

Treatment	Subject	Planned Relative Time	Date/Time	Chloride (MMOL/L)			Glucose (MMOL/L)			Potassium (MMOL/L)			Sodium (MMOL/L)		
				Result	RI	BL	Result	RI	BL	Result	RI	BL	Result	RI	BL

Treatment	Subject	Planned Relative Time	Date/Time	Calcium (MMOL/L)			Creatinine (UMOL/L)			Etc.		
				Result	RI	BL	Result	RI	BL	Result	RI	BL

RI for Reference Interval flag, BL for Change from Baseline flag;

H = Above reference interval, L = Below reference interval, I = Increase from baseline greater than pre-defined limit, D = Decrease from baseline greater than pre-defined limit

Programming notes: Lists only double-flagged subjects
 Include all parameters for the study following the order from the lab report (above is a guide only)

Template L_URI_PG

Listing 16.2.x.xx Listing of urinalysis data

Treatment	Subject	Planned Relative Time	Date/Time	Specific Gravity		pH		Protein		Glucose	
				Result	RI	Result	RI	Result	RI	Result	RI

RI for Reference Interval flag, H = Above reference interval, L = Below reference interval, A = Abnormal result

Programming notes: Include all parameters for the study following the order from the lab report (above is a guide only)

Template L_VS1_PG

Listing 16.2.x.xx Listing of vital signs of potential clinical importance

Treatment	Subject	Planned Relative Time	Date/Time	Systolic	Diastolic	Etc (units)
				Blood Pressure (mmHg)	Blood Pressure (mmHg)	
		24 H	26SEP2012:09:57	63	148*	

* Value of potential clinical importance

Template L_EG1_PG

Listing 16.2.x.xx Listing of ECG values of potential clinical importance

Treatment	Subject	Planned Relative Time	Date/Time	Heart Rate (bpm)	PR Int. (msec)	QRS Dur. (msec)	QRS Axis (deg)	QT Int. (msec)		QTcB (msec)		QTcF (msec)	
								Observed	Change from Baseline	Observed	Change from Baseline	Observed	Change from Baseline
		24 H	26SEP2012:09:57	63	148	78	50	390	32.7 *	399	-27.7	396	-6.5

* Value of potential clinical importance

Programming notes: Do not list RR

Template L_EG2_PG

Listing 16.2.x.xx Listing of abnormal ECG findings

Treatment	Subject	Planned Relative Time	Date/Time	ECG Finding	Comment on Clinical Significance
-----------	---------	-----------------------	-----------	-------------	----------------------------------

Programming notes: Lists only values with Normal variant='No' or with comment on ECG result
ECG Finding contains Physician's Opinion from CRF and relates to whole trace (not individual parameters), e.g. Normal, Abnormal - NCS or Abnormal - CS

Template L_PE1_PG

Listing 16.2.x.xx Listing of abnormal physical examination findings

Treatment	Subject	Planned Relative Time	Date/Time	Site	Details
-----------	---------	-----------------------	-----------	------	---------

Programming Notes: List only findings with an 'abnormal' result.
If subjects have multiple abnormal sites at a given time, create a separate row for each site.
For ophthalmology listing replace column Site with Test.

Template L_NE1_PG

Listing 16.2.x.xx Listing of abnormal neurological examination findings

Treatment	Subject	Planned Relative Time	Date/Time	Type	Assessment	Details
-----------	---------	--------------------------	-----------	------	------------	---------

Programming Notes: *Type = (Mental Status, Cranial Nerves ,etc.)*
List only findings with an 'abnormal' result.
If subjects have multiple abnormal assessment at a given time, create a separate row for each assessment.

Appendix A: Laboratory Ranges

Pre-determined Changes for Laboratory Data (from FL140 v4)

Test	Test Code	Unit	Sex	Delta ranges	
				Acceptable decrease	Acceptable increase
Activated partial thromboplastin time	APTTT	sec	Both	- 8.0	+ 8.0
Alanine transferase	ALTN	IU/L	F	-	+ 30
Alanine transferase	ALTN	IU/L	M	-	+ 30
Albumin	ALB	g/L	Both	- 8	+ 8
Alkaline phosphatase	ALPN	IU/L	Both	- 30	+ 30
Amylase	AMY	U/L	Both	-	+ 150
Aspartate transferase	ASTN	IU/L	F	- 30	+ 30
Aspartate transferase	ASTN	IU/L	M	- 30	+ 30
Basophils	BASO	10 ⁹ /L	Both	-	+ 0.30
Bilirubin conjugated	DBIL	µmol/L	Both	-	+ 4.0
Bilirubin total	TBIL	µmol/L	F	- 20.0	+ 10.0
Bilirubin total	TBIL	µmol/L	M	- 20.0	+ 10.0
Bilirubin unconjugated	IBIL	µmol/L	Both	-	-
C-reactive protein	CRP	mg/L	Both	-	-
CK relative index	CKMBR	%	Both	-	-
Calcium	CA	mmol/L	Both	- 0.4	+ 0.4
Carbon dioxide	CO2	mmol/L	Both	- 8	+ 8
Chloride	CL	mmol/L	Both	- 10	+ 10
Cholesterol	CHOL	mmol/L	Both	-	+ 0.7
Creatine kinase	CK	IU/L	F	-	+ 400
Creatine kinase	CK	IU/L	M	-	+ 400
Creatinine	CREA	µmol/L	Both	-	+ 40
Creatinine (DOA urine)	CREDA-U	mmol/L	Both	-	-
Eosinophils	EOS	10 ⁹ /L	Both	-	+ 0.50
Erythrocyte sedimentation rate	ESR	mm/h	Both	-	-
Fibrinogen	FIB-C	g/L	Both	-	-
Free T3	FT3	pmol/L	Both	- 3.5	+ 3.5
Free T4	FT4	pmol/L	Both	- 15.0	+ 15.0
Gamma glutamyl transferase	GGT	IU/L	F	-	+ 40
Gamma glutamyl transferase	GGT	IU/L	M	-	+ 40
Globulin	GLOB	g/L	Both	- 8	-
Glucose	GLU	mmol/L	Both	- 1.5	+ 2.5
Haematocrit	HCT	L/L	Both	- 0.050	-
Haemoglobin	HB	g/L	Both	- 20	-
High density lipoprotein	HDL	mmol/L	Both	- 1.50	+ 1.50
International normalised ratio	INRR	ratio	Both	-	-
Lactate dehydrogenase	LDH	IU/L	Both	-	+ 150
Lymphocytes	LYMP	10 ⁹ /L	Both	- 1.50	+ 1.50
Magnesium	MG	mmol/L	Both	-	-
Mean cell haemoglobin	MCH	pg	Both	- 2.0	+ 2.0
Mean cell haemoglobin concentration	MCHC	g/L	Both	- 25	+ 25
Mean cell volume	MCV	fL	Both	- 10	+ 10

Test	Test Code	Unit	Sex	Delta ranges	
				Acceptable decrease	Acceptable increase
Monocytes	MONO	10 ⁹ /L	Both	- 0.50	+ 0.50
Neutrophils	NEUT	10 ⁹ /L	Both	- 2.00	+ 8.00
Phosphate	PHOS	mmol/L	Both	- 1.00	+ 1.00
Platelets	PLT	10 ⁹ /L	Both	- 100	+ 100
Platelets (citrate tube)	PLTC	10 ⁹ /L	Both	- 100	+ 100
Potassium	K	mmol/L	Both	- 0.8	+ 0.8
Prolactin	PROL	µg/L	Both	-	-
Prothrombin time	PTT	sec	Both	- 4.0	+ 4.0
Red blood cells	RBC	10 ¹² /L	Both	- 1.0	-
Reticulocyte	RET	%	Both	-	-
Reticulocyte count	RETC	10 ⁹ /L	Both	-	-
Reticulocyte manual count	RETM	10 ⁹ /L	Both	-	-
Sodium	NA	mmol/L	Both	- 8	+ 8
Thrombin time	TT	sec	Both	-	-
Thyroid stimulating hormone	TSH	mIU/L	Both	- 3.00	+ 3.00
Total protein	TP	g/L	Both	- 15	-
Triglycerides	TG	mmol/L	Both	-	+ 1.5
Urea	UREA	mmol/L	Both	- 5.0	+ 2.0
Uric acid	UA	µmol/L	Both	- 100	+ 100
Urine pH	UPH	N/A	Both	- 4	+ 4
Urine red blood cells	URBC	10 ⁶ /L	Both	-	+ 10
Urine white blood cells	UWBC	10 ⁶ /L	Both	-	+ 100
White blood cells	WBC	10 ⁹ /L	Both	- 2.0	+ 8.0

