Several reproductive and developmental toxicity studies were conducted in rats and rabbits. Effects of emodepside on reproductive performance in rats occurred only at parentally toxic doses. No primary effect on fertility and reproduction was observed. In this species, both ovarian weight and gestation rate were unaffected by treatment. Primary systemic parental effects were due to diabetes I like effects, which were well known from repeat dose studies in rats. A battery of well-conducted, GLP-compliant teratogenicity studies revealed maternal toxicity, fetotoxicity, foetal malformations and various skeletal/visceral anomalies or deviations. Clinical signs of systemic maternal toxicity were evident at dose rates ≥ 6 mg/kg. Overall, severe maternal toxicity at 18 mg/kg resulted in adverse effects on foetal development. The NOAEL for maternal toxicity in rats was 2 mg/kg and the NOAEL for developmental toxicity was 0.5 mg/kg. However, as discussed above, diabetes like effects, which were not measured in developmental toxicity studies, occurred in lower dosages. Therefore, it can be assumed that the maternal toxic dose was significantly lower (NOEL of 1 mg/kg in safety pharmacology studies on glucose levels in the blood. See also glucose level in pregnant rats). In rabbits, the effects were similar to the rat studies. The NOEL for developmental toxicity in the rabbit was 5 mg/kg.

Additional endocrinology studies confirmed the involvement of emodepside in hormone deregulation (reduced estradiol [E2], triiodothyronine [T3], insulin, leptin and prolactin levels and enhanced thyroid-stimulating hormone [TSH] and glucagon levels) while not having estrogenic/anti-estrogenic or androgenic/anti-androgenic potency. This deregulation is assumed to be the cause for the observed developmental toxicity.

In vitro and *in vivo* genotoxicity studies revealed no mutagenic potential for emodepside; no carcinogenicity studies were conducted. Local tolerance studies in rats and rabbits revealed no skin- or eye-irritating potential of emodepside. In guinea pigs, emodepside was found to have no skin sensitization potential.

General Pre-Clinical Summary

The non-clinical data package of emodepside is comprehensive due to the authorization of 3 veterinary medicinal products (Profender Spot-on, Profender

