12.4 Values of Potential Clinical Importance

Any laboratory value outside the reference interval for that variable will be flagged with an 'H' if it is higher than the reference interval, and with an 'L' if it is lower. Additionally, if, during the course of the trial, a variable changes from baseline (Day 0 pre dose) by more than a predetermined amount (as defined by the Principal Investigator, Appendix A), that value will receive a flag 'I' if increased, or 'D' if decreased. Therefore, if a value both falls outside the reference interval and alters from the baseline value by more than the predetermined amount, it will attract a double flag and will be considered to be potentially clinically important.

A vital signs result will be considered to be of potential clinical importance if it falls outside the relevant range below:

Vital Sign	Range
Supine/semi-recumbent systolic blood pressure	85–160 mm Hg
Supine/semi-recumbent diastolic blood pressure	40–90 mm Hg
Supine/semi-recumbent heart rate	35–100 beats/min
Respiration rate	8–20 per min
Oral temperature	35.5–37.8°C

QT, QTcB or QTcF > 450 msec and increases in QT, QTcB or QTcF from baseline of > 30 msec will be considered to be potentially clinically important.

13 Study Population

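### The Appendix A decrease limits for free T4 and free T3 leave the double flag almost unable to count falls of up to about 50%

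*SAP*

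**What the plan says.** SAP 12.4 gives two separate flags. A result outside the reference interval gets 'H' or 'L'. A result that "changes from baseline (Day 0 pre dose) by more than a predetermined amount (as defined by the Principal Investigator, Appendix A") gets 'I' or 'D'. Potential clinical importance needs both: "if a value both falls outside the reference interval and alters from the baseline value by more than the predetermined amount".

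SAP Appendix A supplies the amounts under the title "Pre-determined Changes for Laboratory Data (from FL140 v4". The thyroid rows are:

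- "Free T3 FT3 pmol/L Both - 3.5 + 3.5"
- "Free T4 FT4 pmol/L Both - 15.0 + 15.0"
- "Thyroid stimulating hormone TSH mIU/L Both - 3.00 + 3.00"

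No derivation is given, and neither document states a reference interval for any of the three tests.

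The double flag drives Table 14.3.4, whose shell (template T_LB1) has columns only for the HI and LD combinations. It also drives Listings 16.2.8.1 and 16.2.8.2, which are limited to double-flagged subjects. Free T3, free T4 and TSH are safety variables in Protocol 2.2.2 and sit under the primary endpoints in SAP 4.2.1.

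Protocol 1.3 reports that animal endocrinology studies showed "reduced estradiol [E2], triiodothyronine [T3], insulin, leptin and prolactin levels and enhanced thyroid-stimulating hormone [TSH] and glucagon levels".

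**The concern.** The change criterion is meant to remove trivial excursions just outside the interval. It does that only if the limit is small relative to usual baseline values. For these two hormones the decrease limit is about as large as a plausible baseline, or a large fraction of one. A concentration cannot fall below zero, so the 'D' half of the double flag may be out of reach for many subjects.

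Reduced T3 is one of the hormone effects that led to thyroid tests being of interest for this drug. If the 'LD' count for free T3 is zero, a reader of Table 14.3.4 would naturally take it as evidence that no important fall occurred. That inference is safe only if the rule could have shown a fall. Cohorts have six active subjects, so the table is meant to pick out individual values that a group mean would dilute.

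**Working it through.** The plan has no calculation of its own to reproduce here; the limits are simply stated.

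**Inputs from the documents.** Decrease limit d = 15.0 pmol/L (free T4) and 3.5 pmol/L (free T3), from SAP Appendix A. Both conditions are required (SAP 12.4).

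**Step 1: documents alone.** Let b be the baseline, f the proportional fall and LLN the lower limit of the reference interval. The new value is b(1 − f).

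- 'D' requires b·f > d, so b > d/f.
- 'L' requires b(1 − f) < LLN, so b < LLN/(1 − f).
- Since f cannot exceed 1, 'D' is impossible when b ≤ d: baselines ≤ 15.0 (free T4) or ≤ 3.5 (free T3).
- For f = 0.5, b must exceed 15.0/0.5 = 30 (free T4) or 3.5/0.5 = 7.0 (free T3).
- A double flag at f = 0.5 also needs b < 2·LLN, so it is possible for someone only if LLN exceeds 15.0 (free T4) or 3.5 (free T3).

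Fall needed for 'D' at example baselines (d/b):

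- free T4: 15/16 = 94%, 15/20 = 75%, 15/22 = 68%
- free T3: 3.5/4.0 = 88%, 3.5/5.0 = 70%, 3.5/6.5 = 54%

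**Step 2: assumed intervals.** These are assumptions, not document figures. Baseline is taken as normal with 95% inside the interval, so mean = midpoint and SD = width/3.92. Every subject falls by the same proportion f. The proportion double-flagged is P(d/f < b < LLN/(1 − f)), or zero if that range is empty.

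Example 1: free T3, interval 4.0–7.0, f = 0.5. Mean 5.5, SD 3.0/3.92 = 0.765. 'D' needs b > 7.0 and 'L' needs b < 8.0, so P = Φ(3.27) − Φ(1.96) = 0.0245.

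Example 2: free T4, interval 12–22, f = 0.5. 'L' needs b < 24 and 'D' needs b > 30. The range is empty, so P = 0, although P(below range) = Φ((24 − 17)/2.551) = 0.997.

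| Test | Assumed interval (pmol/L) | Below range, 50% fall (%) | Double-flagged, 50% fall (%) | 60% fall (%) | 70% fall (%) |
|---|---|---|---|---|---|
| Free T4 | 7–16 | 86.2 | 0 | 0 | 0 |
| Free T4 | 9–19 | 94.2 | 0 | 0 | 0.2 |
| Free T4 | 10–20 | 97.5 | 0 | 0 | 0.6 |
| Free T4 | 12–22 | 99.7 | 0 | 0.1 | 4.1 |
| Free T4 | 11–25 | 86.9 | 0 | 2.1 | 16.9 |
| Free T3 | 2.5–5.5 | 90.4 | 0 | 0.7 | 9.6 |
| Free T3 | 2.6–5.7 | 90.8 | 0 | 1.5 | 14.1 |
| Free T3 | 3.1–6.8 | 90.7 | 0 | 17.3 | 47.9 |
| Free T3 | 3.5–6.5 | 99.6 | 0 | 13.8 | 50.0 |
| Free T3 | 4.0–7.0 | 99.9 | 2.45 | 33.2 | 74.3 |

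Falls of 30% and 40% give 0% double-flagged in every row.

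**Step 3: per cohort.** The chance that at least one of six active subjects is double-flagged is 1 − (1 − p)^6. For free T3 and a 50% fall it is 0 to 14% (1 − 0.9755^6 = 0.138). For a 60% fall it is 4% to 91%, depending on the interval.

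**The case against.** Several stronger readings are tempting, and the documents do not support them.

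- **A low thyroid hormone can almost never be flagged.** A reader might infer this for both tests. For free T3 it fails for large falls: 60% gives 0.7 to 33% double-flagged and 70% gives about 10 to 74%. With an interval of 3.1–6.8 the width (3.7) exceeds the limit (3.5), so a subject starting at the upper limit is double-flagged by any below-range value. The single 'L' flag has no change condition at all.
- **A 40% fall such as 5.0 to 3.0 in free T3 is a missed abnormality.** Under two of the five assumed intervals (2.5–5.5 and 2.6–5.7), 3.0 is in range and would not be 'L' under any change limit.
- **The limits are wrong in both directions.** The argument rests on the floor at zero and concerns decreases only. Nothing here counts against the increase limits.
- **The animal data point to T4.** Protocol 1.3 names T3 and TSH, not T4. The arithmetic is strongest for free T4, while the animal signal is for T3. Raised TSH has its own limit of 3.00 mIU/L, which meets no floor on the increase side.
- **Low values would disappear from the report.** They would not. Table 14.3.5.1 (template T_LB2) gives values and changes by treatment and time, with minimum and maximum. SAP 18.1 promises complete listings. Protocol 8.5.5 has confirmed abnormal results assessed for clinical significance. A subject double-flagged on another chemistry test would have all chemistry shown in Listing 16.2.8.2.

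It is also fair to say that no document calculation is wrong, that SAP 12.4 leaves the amounts to the Principal Investigator, and that how specific a flag should be is partly judgement. All of this stands and narrows the point. It does not restore the function of Table 14.3.4, which exists to count individual important values.

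**Conclusion.** The point holds in a limited form. From the documents alone, the 'D' flag is impossible at baselines of 15.0 pmol/L or below for free T4 and 3.5 pmol/L or below for free T3, and a halving needs a baseline above 30 or 7.0 pmol/L. How many subjects this affects depends on reference intervals that the documents do not give. Over assumed upper limits of 16–25 (free T4) and 5.5–7.0 pmol/L (free T3), with normal baselines and a uniform proportional fall, a 50% fall is below range in most subjects and double-flagged in 0% for free T4 and 0 to about 2.5% for free T3. For larger free T3 falls the rule works in part.

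An empty 'LD' entry for these hormones would therefore say little about falls of up to about half of baseline. This is a weakness in one summary table and the abbreviated listings. It is not a loss of data, nor a gap in the review of individual subjects.

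**What to change.** Before the first unblinding (Cohorts 1 and 2), amend SAP 12.4 and Appendix A so that any free T3 or free T4 value below the reference interval, in a subject whose baseline was in range, is counted in Table 14.3.4 and listed as potentially clinically important regardless of the change limit. Under a 50% fall this would capture nearly all of the below-range subjects in the table above, apart from the few whose baseline was already out of range.

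Alternatively, state the laboratory's free T3 and free T4 reference intervals in Appendix A and have the Principal Investigator reset the two decrease limits against them. The increase limits and the TSH row can stay.

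The cost is two table rows and a sentence in 12.4. No sample or procedure changes. Protocol 10.6.2 carries the same double-flag rule, but Protocol Section 10 allows the SAP to modify the planned methods, and SAP Section 3 provides for stating the difference. The downside is a few more flagged values, including some from subjects who start near the lower limit and drift just below it.
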